#### **4.4 Early Withdrawal of Subjects**

##### **4.4.1 When and How to Withdraw Subjects**

During this study, medical history will be taken periodically as mentioned in the schedule of events. Physical examinations and neurological examinations will be conducted every study visit except for the 4-week flexible titration (2 mg/week, up to 8mg) visit. Protocol directed screening for adverse events will be performed at each visit.

The Principal and Co-Investigator as well as Study Coordinator are responsible for individual safety monitoring. Stopping or interruption of the study may be necessary if a significant number of study participants develop unexpected clinical flaring or significant worsening that appears temporally linked with PER administration to be used for the indication outlined in this protocol.

The Principal Investigator and/or Investigator will review all adverse event reports to determine if specific reports need to be made to the IRB and FDA. For this study, all SAEs or possible UPIRTSOs will be reported to the IRB.

##### **4.4.2 Data Collection and Follow-up for Withdrawn Subjects**

All study data will be stored in the password protected REDCAP database. Access to the REDCAP database will be limited to the Principal Investigator, Investigators and Statistician. Paper documents, including patient seizure logs/diaries and case report forms, will be kept in a locked cabinet with access available only to the Investigators and Study Coordinator.

The sponsor-investigator will maintain records and essential documents related to the conduct of the study for a period of 2 years after completion of the study. These will include subject case histories and regulatory documents. All study data will be collected and managed using REDCap electronic data capture tools hosted at the Mayo Clinic. REDCap (Research Electronic Data Capture) is a secure, web-based application designed to support data capture for research studies, providing 1) an intuitive interface for validated data entry; 2) audit trails for tracking data manipulation and export procedures; 3) automated export procedures for seamless data downloads to common statistical packages; and 4) procedures for importing data from external sources.

## 5 Study Drug

### 5.1 Description

PER is a noncompetitive AMPA glutamate receptor antagonist.

### 5.2 Treatment Regimen

Patients will begin on PER 2 mg PO and increase in weekly intervals of 2 mg/week until reaching minimum dose of at least 4 mg/day and a maximum of 8 mg/day per patient. Alternative ASDs will be instituted according to best clinical practice and without excessive dosing beyond standard doses approved by the U.S. Food and Drug Administration. Participants will be assigned to receive open label PER or an alternate ASD for 40 weeks. The frequency of oral delivery of PER will be every 24 hours but no more frequently than every 12 hours. The route of drug delivery will be orally administered (PO). The other ASDs will be chosen and be administered according to prior exposure to ASDs and according to best clinical practice.

### 5.3 Method for Assigning Subjects to Treatment Groups

Participants will be assigned to receive:

Group A: open label arm of adjunctive PER (study drug) for patients with seizures treated with at least 1 ASD administered in escalating divided doses of 2 mg/week to 4 mg daily with flexible dosing to 8 mg/day by 4 weeks. Subjects must undergo forced titration of 2 mg/week and be able to tolerate 4 mg to continue in the study. Concomitant ASD will be utilized according to best clinical practice.

or

Group B: continued open label treatment for patients with seizures treated with at least 1 ASD, as per best medical practice, without the use of PER.

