Study Product, Dose, Route, Regimen	PER is a noncompetitive AMPA glutamate receptor antagonist. The two phases of the treatment portion of this study include a titration phase and a stable dosing phase. This study will have two treatment arms consisting of PER and alternative ASD arm. The PER arm will begin a titration phase with 2mg PER PO q.d. (may be split to b.i.d.) for one week and increase by 2mg/week until reaching an initial dose of 4mg PO q.d. (q.d. or b.i.d. dosing) is reached. Flexible dosing of PER above 4mg to a maximum of 8 mg daily will be compared to use of alternative ASDs and be guided by best clinical practices with dosing and indication within U.S. FDA guidelines.
Duration of Administration	Participants will be assigned to receive open label PER or an alternate ASD for at least 12 week and up to 40weeks for the remainder of the study. This includes 2-4 weeks of titration and up to 40 weeks of stable dosing. Reduction by 2 mg will be allowed in cases of efficacy if doses greater than 4 mg daily result in non-idiopathic side-effects.
Reference therapy	All comparisons will use standard ASDs as the reference therapy using an intent to treat study design for patients initiating or tapering off PER therapy.
Statistical Methodology	Statistical analysis will include Student T-test, Chi-square for categorical differences. An interim analysis will be performed when half of the targeted subjects are enrolled.

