### **3.4 Primary Endpoints**

- A. The number of patients with a high-grade glioma who achieve a > 50% reduction in focal seizures with PER 4 mg daily after failing 1 or more ASDs at 3 and 6 months.
  1. The overall survival of patients with high-grade glioma treated with PER at 3 months.
  2. Decline in neuropsychological function at 6 months.

All comparisons will use intent to treat model for patients initiated or exiting PER therapy. In event of patients not surviving till 12 months, most recent data prior to death will be used for correlation.

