### **3.5 Identification of Source Data**

Electronic medical records will be maintained via a RedCAP database for consecutive and prospective collection of data.

Efficacy measures used in the study include: clinical assessments will include serial brain MRI, EEG, anti-seizure drug levels and subject self-assessment at clinical follow-up; Neurological Disorders Depression Inventory for Epilepsy (NDDI-E), assessment for screening of depression PHQ-9;Montreal Outcome Cognitive Assessment (MOCA); Clinical Global Impression of Change (CGIC) score; Columbia –Suicide Severity Rating Scale. Seizure calendars performed at 2 months prior to initiation of therapy or adequate reliable historical baseline, and then monthly during study; and QOLIE-31, (see schedule of events for frequency of assessment).

Anatomic brain MRI with perfusion scanning/gadolinium will be obtained at 3 months and then every 3 months, to examine the correlated progression of brain tumor, or the absence of tumor. Laboratory studies will be employed before and after PER initiation. EEG will be obtained at baseline and at 3 months and 12 months to identify changes in background activity (e.g. diffuse slowing) and epileptiform discharges to correlate with focal seizure presence vs absence. Neuropsychological batteries will determine the presence or absence of significant anxiety, depression or cognitive changes over time and quality of life inventory will be obtained at the beginning, intermediate and end of the trial.

The following source data will be directly recorded on the Case Report Form (CRF):

- A comprehensive History and Physical examination and Neurological examination will occur at the initial screening/baseline.
- Clinical visitation will occur at screening/baseline, 3, 6, and 12 months.

Survey questionnaires will be obtained at baseline, 3, 6, 9, and 12 months. The following source data will not be directly collected in the Case Report Form (CRF), but will be captured in supportive documentation (study source documents, EMR):

- Laboratory studies will be employed at baseline and at each clinical visit after PER initiation.
- Brain tumor tissue will be assessed for the usual molecular markers (i.e., IDH-mutant vs wildtype, MGMT methylation, ARX).
- 12-lead ECG will be obtained at baseline and as clinically indicated
- Anatomic brain MRI with and without gadolinium will be obtained at baseline and follow-up brain MRI at 3 months and 6 months during PER use.

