- EEG will be obtained at baseline and at 3 months and 12 months to identify changes in background activity (e.g. diffuse slowing) and epileptiform discharges to correlate with focal seizure presence vs absence.
- Neuropsychological batteries will be obtained at baseline, 3 months, and 6 months to determine the presence or absence of significant neurocognitive decline.

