#### **4.3 Subject Recruitment, Enrollment and Screening**

Subjects (n = 20), will be male and female adults with a high-grade glioma recruited from Mayo Clinic in Jacksonville, Florida- [name], DO, (PI). 10 subjects will be enrolled into an adjunctive Perampanel and other ASDs group, and 10 subjects will receive only alternative ASDs. There will be a 6-month recruitment period for screening and enrollment. The treating physician will decide, based on best medical practice, which patients are candidates for adjunctive Perampanel and other ASDs, or only alternative ASDs. Patients taking Perampanel will begin their titration phase upon enrollment.

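### Group A patients who cannot tolerate 4 mg perampanel leave the study, not just the drug, and so miss every follow-up MRI and neuropsychology visit and the 3-month MOCA

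*Combined protocol and SAP*

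**What the plan says.** Section 5.3 sets the condition for Group A: "Subjects must undergo forced titration of 2 mg/week and be able to tolerate 4 mg to continue in the study". Section 4.3 places it after entry: "Patients taking Perampanel will begin their titration phase upon enrollment". The Group B paragraph of 5.3 has no comparable condition. Sections 1.5 and 5.2 make 4 mg/day the minimum dose, and the Study Summary allows dose reduction only from doses above 4 mg, so no lower dose keeps an intolerant patient in the study.

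Section 4.4.2 is headed "Data Collection and Follow-up for Withdrawn Subjects", but its text covers only data storage, access, record retention and the database. Section 4.4.1 does not separate stopping PER from leaving the study, and the Schedule of Events has no early-termination or off-drug visit.

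On analysis, section 3.4 states "All comparisons will use intent to treat model for patients initiated or exiting PER therapy", and the Reference therapy row of the Study Summary describes "using an intent to treat study design for patients initiating or tapering off PER therapy". Section 7.3 names a protocol-compliant population without saying whether it is primary or supportive. The only rule for incomplete follow-up concerns deaths: "In event of patients not surviving till 12 months, most recent data prior to death will be used for correlation".

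**The concern.** The primary objective is the efficacy and safety of PER compared with alternate ASDs. The secondary objectives compare neurocognitive change and MRI progression between the same groups, and 3.4 lists 6-month neuropsychological decline under the primary endpoints. A rule that ends participation for PER-intolerant patients selects Group A on tolerability after treatment has begun, while Group B is not selected in this way. The MRI and cognition comparison then sets PER tolerators against all Group B patients.

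The plan says it wants patients who exit PER in every comparison, but 5.3 ends the data collection that this needs. Section 7.1 presents the study as a pilot for a larger multi-center trial. That trial would need to know what happens to patients who fail titration, as well as how many do.

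**Working it through.** The plan gives no intolerance rate, response rate or effect size, so it has no figure of its own to reproduce. The main check sets the schedules side by side and needs no assumed rate.

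**Step 1. What a patient leaving by Day 30 misses.** The Schedule of Events runs titration to Day 30.

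| Assessment | Post-baseline times | Source | Planned | Kept |
|---|---|---|---|---|
| MRI | months 3, 6 | 3.5, source-data list | 2 | 0 |
| MRI | Days 90, 180, 300 | Schedule of Events | 3 | 0 |
| MRI | months 3, 6, 9, 12 | 3.5, efficacy-measures text | 4 | 0 |
| Neuropsychology | months 3, 6 | 3.5 | 2 | 0 |
| Neuropsychology | Days 90, 180, 300 | Schedule of Events; 6.8, 6.11, 6.15 | 3 | 0 |
| MOCA | Days 7, 14, 21, 30, 90, 180, 300 | Schedule of Events; section 6 | 7 | at most 4 |

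The 3.5 entry for neuropsychology reads "Neuropsychological batteries will be obtained at baseline, 3 months, and 6 months". The first MRI or neuropsychology follow-up comes 90 − 30 = 60 days after titration ends. Visit 5 (Day 21) mentions reviewing an MRI, but the Schedule has no new scan then. At least 7 − 4 = 3 MOCAs are lost, including the 3-month one on which the hypothesis in 7.2 depends.

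**Step 2. Whether another provision supplies these data.**
- Adverse events: yes. Unresolved events are followed (8.1, Post-study Adverse Event), and the reporting period runs 12 months after the last dose (8.1).
- Deaths: perhaps, passively. Death is a serious adverse event (8.1), and 4.4.1, 8.4 and the monitoring plan in section 10 send all serious adverse events to the IRB. Section 8.2 is narrower: in the reporting period it requires immediate reporting only of events at least possibly related.
- Vital status: sought only from subjects who revoke authorization (9.1).
- Missing data: the text under that heading in 7.2 gives no rule for leavers.
- Number failing titration, and why: recoverable from adverse event, drug reconciliation and CRF records (5.9.3, Schedule of Events, 9.3).

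**Step 3. The responder result.** Let R of 10 Group A patients respond if all are followed, and let k leave, r of them responders. The rate among those remaining is (R − r)/(10 − k), which exceeds R/10 only if r/k < R/10. R, k and r are assumptions.

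| R (r = 0) | k = 1 | k = 2 | k = 3 |
|---|---|---|---|
| 3 (30%) | 3/9 = 33.3% | 3/8 = 37.5% | 3/7 = 42.9% |
| 4 (40%) | 4/9 = 44.4% | 4/8 = 50.0% | 4/7 = 57.1% |
| 5 (50%) | 5/9 = 55.6% | 5/8 = 62.5% | 5/7 = 71.4% |

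The rise is 3.3 to 21.4 points. Endpoint A counts responders on PER 4 mg, so a leaver cannot qualify and r = 0. If response were scored from the diary whatever drug is taken, the direction could reverse: R = 4, k = 2, r = 1 gives 3/8 = 37.5%, a fall of 2.5 points. The exact 95% interval for 4/10 is 12.2% to 73.8%, which contains all these values.

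**Step 4. How often the rule would apply.** With an assumed intolerance rate p, the chance that at least one of 10 leaves is 1 − (1 − p)^10: 40% at p = 5%, 65% at 10%, 89% at 20% and 97% at 30%.

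**The case against.** The strongest reply is that the plan already intends to analyse these patients, since 3.4 and the Study Summary apply intent to treat to those exiting or tapering off PER. On this view 5.3 is a drafting conflict to clarify. This stands for the responder count, but an analysis principle does not create scans or cognitive tests that nobody scheduled. Clinical scans may exist in the medical record, but the plan does not say they will be used.

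Three stronger readings are tempting, and the documents do not support them.
- A reader might infer that survival of leavers goes unrecorded. Deaths within 12 months of the last dose may reach the study as serious adverse events, so the supported statement is that active vital-status follow-up is absent.
- A reader might take "follow-up brain MRI at 3 months and 6 months during PER use" as a ban on off-drug scans. Read literally it would also cancel Group B's MRIs, yet section 2 compares MRI progression between groups and the Schedule restricts only drug dispensing and accountability to the PER arm. It is loose drafting.
- A reader might infer that Endpoint A is biased or cannot be computed. Its count needs no off-drug data, and 7.3 does not say that its population replaces intent to treat.

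It is also fair to say that this is an unpowered pilot of 20 (7.1) with physician-chosen arms (4.3), so complete follow-up would not make the comparison unbiased. That limits the weight of the point, but the lost assessments remain avoidable.

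**Conclusion.** The point holds, and the plan should be changed. Followed as written, section 5.3 costs the study all follow-up MRI, all follow-up neuropsychology and the 3-month MOCA for any Group A patient who fails titration, with no matching loss in Group B. The Group A side of those comparisons then describes PER tolerators only. This rests on reading 5.3 literally, as exit from the study, and on departure by Day 30. It needs no assumed rate.

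The number affected, and the size of any bias in the MRI and cognition results, cannot be derived from the documents. The responder percentages above are illustrations: they apply only if the protocol-compliant population is used, and they lie within sampling error. The plan should not be read as neglecting the safety of leavers or as leaving their deaths wholly unrecorded. Confidence in the overall point is medium, because 5.3 and the intent-to-treat statements conflict and the plan does not say which governs.

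**What to change.** 1. Section 5.3: a Group A patient who cannot tolerate 4 mg stops PER but stays in the study. If doses below 4 mg are to be allowed instead, amend the minimum in 1.5 and 5.2 as well.
2. Section 4.4.2: unless consent is withdrawn, such patients keep the scheduled visits, seizure diary, MRI, cognitive assessments and vital-status follow-up.
3. Section 3.5: reword the follow-up MRI entry so that it plainly covers both groups and patients off PER.
4. Section 7.3: make the primary analysis all enrolled patients by assigned group, with the same rule for treatment discontinuation in both groups. Two even-handed choices are to score both groups from the observed diary whatever drug is taken, or to count stopping for intolerance as non-response in both. Counting only PER-intolerant patients as non-responders would tilt the comparison against PER. Keep the protocol-compliant analysis as supportive, and report how many fail titration and why.

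The cost is a short amendment to four sections, using visits already scheduled. A few patients are followed off drug, and the PER estimate may be less favourable. Bias from physician-chosen allocation remains.

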### 5.4 Preparation and Administration of Study Drug

PER (to be used for the indication outlined in this protocol) will be shipped by Eisai to the Mayo Clinic research pharmacy in Florida. Upon receipt, an inventory will be performed, and a drug receipt log filled out by the person accepting the shipment. Designated study staff will count and verify that the shipment contains all the items noted on the shipping invoice. Any discrepancies, damaged or unusable drug in any given shipment will be documented in the study files. The Investigators must be notified immediately of any discrepancies, damages or unusable products that are received.

### 5.5 Subject Compliance Monitoring

Anti-seizure drug levels will be evaluated at clinical follow-up (see study schema for frequency of assessment).

### 5.6 Prior and Concomitant Therapy

Concomitant therapy will allow 0-3 concomitant ASDs. No specific drugs will be disallowed; concomitant ASDs and non-ASDs (e.g. narcotics, benzodiazepines, and barbiturates) will serve as exclusionary therapies when deemed clinically relevant according to best clinical practice.

### 5.7 Packaging

Study drug will be packaged according to the manufacturer's approval for use by the U.S. FDA.

Bottles containing 20 tablets of 4 mg dosages of PER are anticipated.

Study drug will be shipped separately by subject-specific packages.

The contents of the package will include study drug and associated approved labelling.

## **5.8 Masking/Blinding of Study**

This is an open-label study.

## **5.9 Receiving, Storage, Dispensing and Return**

Study drug will be received by the principal investigator and stored in a secured location. Unused medication will be returned to the study institution and returned to Eisai Pharmaceuticals.

### **5.9.1 Receipt of Drug Supplies**

Perampanel (to be used for the indication outlined in this protocol) will be shipped by Eisai to the Mayo Clinic research pharmacy in Florida. Upon receipt, an inventory will be performed and a drug receipt log filled out by the person accepting the shipment. Designated study staff will count and verify that the shipment contains all the items noted on the shipping invoice. Any discrepancies, damaged or unusable drug in any given shipment will be documented in the study files. The investigators must be notified immediately of any discrepancies, damages or unusable products that are received.

### **5.9.2 Storage**

Perampanel will be stored at Mayo Clinic research pharmacy in Florida. Medication will be stored at room temperature (between 68 and 77° F) with limited exposure to heat, moisture, and light.

### **5.9.3 Dispensing of Study Drug**

Regular study drug reconciliation will be performed to document drug assigned, drug dispensed, drug returns, and drug remaining. This reconciliation will be logged on the drug reconciliation form and signed and dated by the study team.

### **5.9.4 Return or Destruction of Study Drug**

At the completion of the study, there will be a final reconciliation of drug shipped, drug dispensed, drug returns, and drug remaining. This reconciliation will be logged on the drug reconciliation form, signed and dated. Any discrepancies noted will be documented and investigated, prior to return or destruction of unused study drug. Drug destroyed on site will be documented in the study files.

## **6 Study Procedures**

### **6.1 Visit 1 (Screening)**

Informed consent is received, and a review of study inclusion/exclusion criteria is conducted. Medical history and physical examination are performed. Neurological examination is performed. Urine Pregnancy test is performed. Seizure Diary is reviewed.

### **6.2 Visit 2 (Baseline)**

CBC, CMP, and ASD trough levels are evaluated. An MRI of the brain with volume measurement is completed. An EEG is taken if there has not been one completed within 3 months of the visit.

Revised 23NOV2022

Neuropsychological baseline visit. Seizure frequency is assessed. PHQ-9, NDDI-E, MOCA, CGIC, C-SSRS and QOLIE-31 are completed.

Screening and Baseline are preferred to be on the same day, but can occur separate days if needed. All screening and baseline events will be completed before Visit 3.

### **6.3 Visit 3**

Seizure frequency is assessed. Seizure Diary is reviewed. PHQ-9, NDDI-E, MOCA, CGIC, C-SSRS and QOLIE-31 are completed. Dispense study drug to participants in Group A (PER arm).

### **6.4 Visit 4**

Seizure frequency is assessed. Seizure Diary is reviewed. PHQ-9, NDDI-E, MOCA, CGIC, C-SSRS and QOLIE-31 are completed. Dispense study drug to participants in Group A (PER arm).

### **6.5 Visit 5**

Seizure frequency is assessed. Seizure Diary is reviewed. CBC, CMP, and ASD trough levels are evaluated. MRI is reviewed. Seizure frequency is assessed. PHQ-9, NDDI-E, MOCA, CGIC, C-SSRS and QOLIE-31 are completed. Dispense study drug to participants in Group A (PER arm).

### **6.6 Visit 6**

Medical history and physical examination are performed. Neurological examination is performed. Seizure Diary is reviewed. Seizure frequency is assessed. PHQ-9, NDDI-E, MOCA, CGIC, C-SSRS and QOLIE-31 are completed. Dispense study drug to participants in Group A (PER arm).

### **6.7 Visit 7**

Visit 7 will be completed by telephone call. Seizure frequency is assessed. Seizure Diary is reviewed. PHQ-9, NDDI-E, CGIC, C-SSRS and QOLIE-31 are completed by asking the participant the questions verbally. The participant will be asked about medical history.

